### 8.2.2 Study Drug Dose and Duration

[REDACTED]  
[REDACTED]  
[REDACTED] Thus, Part A of the current study is designed to demonstrate safety and efficacy of an 85 µg dose of VX-371 administered twice daily, with or without HS, by oral inhalation in patients with PCD.

Parion Sciences Study PS-G201 was a randomized, double-blind, placebo-controlled, parallel-group study to evaluate the safety and efficacy of 85 µg VX-371 twice daily in subjects with CF. [REDACTED]  
[REDACTED]  
[REDACTED]

In Part B, subjects will continue on their inhaled study drug regimen from Treatment Period 2, and will also receive 150 mg of ivacaftor every 12 hours (q12h) for 28 days through Day 113 (see the Ivacaftor Investigator's Brochure for additional details supporting the efficacy, safety, and pharmacokinetic (PK) profile of ivacaftor).

### 8.2.3 Rationale for Study Assessments

**Spirometry:** Spirometry (as measured by FEV1) is the most widely implemented standardized assessment to evaluate lung function. FEV1 obtained from spirometry is a reflection of the extent of airway obstruction and, as the most clinically accepted measure of disease progression in CF, indicates that FEV1 may be an equally acceptable measure in efficacy studies of the PCD population.

**QOL-PCD:** The QOL-PCD is a subject-completed, disease-specific instrument designed to measure impact on overall health, daily life, perceived well-being and symptoms that has been developed specifically for use in subjects with a diagnosis of PCD.

**SGRQ:** The SGRQ is a 50-item questionnaire with 76 weighted responses. This questionnaire measures health status (quality of life) in patients with diseases of airway obstruction. It has good discriminative and evaluative properties and is responsive to therapeutic trials.

The items in the SGRQ are divided into 3 domains: “Symptoms,” which is concerned with frequency and severity of respiratory symptoms; “Activity,” which is concerned with activities that cause or are limited by breathlessness; and “Impacts,” which covers aspects concerned with social functioning and psychological troubles resulting from airway disease. A score will be calculated for each domain and a total score will also be calculated. For each domain and for the total score, the range of values is 0 to 100, with higher values corresponding with greater impairment of quality of life. A minimum change in score of 4 units was established as clinically relevant after patient and clinician testing.

[REDACTED]

## 9 STUDY POPULATION

[figure not shown]
Eligibility will be reviewed and documented by an appropriately qualified member of the investigator’s team before subjects are enrolled.

### 9.1 Inclusion Criteria

Subjects who meet all of the following inclusion criteria will be eligible.

1. Subject (or subject’s legally appointed and authorized representative) will sign and date an informed consent form (ICF) and, where appropriate, assent form.
2. Willing and able to comply with scheduled visits, treatment plan, study restrictions, laboratory tests, contraceptive guidelines, and other study procedures.
3. Willing and able to use the nebulization device as directed by the instructions for use.
4. The subject must have evidence supportive of a PCD diagnosis, based on the following [REDACTED].

[REDACTED]

5. Subjects with ppFEV1 of  $\geq 40$  to  $< 90$  percentage points adjusted for age, sex, and height according to the Global Lung Function Initiative (GLI) predicted values at the Screening Visit, taken 4 hours or more after last dose of short-acting bronchodilators ( $\beta$ -agonists and/or anticholinergics)
6. Non-smoker for the past 90 days prior to the Screening Visit and less than a 5 pack-year lifetime history of smoking, and willing to not smoke while enrolled in the study.
7. Stable regimen of medications and chest physiotherapy for the 28 days prior to Day 1, and no anticipated need for changes during the study period (other than stopping inhaled HS).
8. If currently using daily inhaled HS, must be able to discontinue its use for the duration of the study.
9. If taking daily chronic or chronic cycling antibiotics, has been on a consistent regimen for at least 4 months prior to the Screening Visit. The cycling regimen of antibiotics can be either intermittent monotherapy (e.g., 28 days on/28 days off) or continuous alternating therapy (e.g., 28-day cycles of 2 alternating antibiotics).
10. Clinically stable (as deemed by the investigator) for at least 14 days prior to the Screening Visit with no evidence of significant new or acute respiratory exacerbations, excluding symptoms of allergic (perennial or seasonal) or non-allergic rhinitis.
11. Female subjects of childbearing potential must have a negative serum pregnancy test at the Screening Visit. Females of childbearing potential must have a negative urine pregnancy test at the Day 1, Day 57, and Day 85 Visits before receiving the first dose of study drug in each Treatment Period, respectively. Subjects of childbearing potential and who are sexually active must meet the contraception requirements outlined in [Section 11.6.5.1](#).

## 9.2 Exclusion Criteria

Subjects who meet any of the following exclusion criteria will **not** be eligible.

1. Diagnosis of CF, including at least 1 of the following:
  - a. Documented sweat chloride test  $\geq 60$  mM by quantitative pilocarpine iontophoresis

- b. Abnormal nasal potential difference (NPD) test
  - c. 2 CF-causing mutations in the CFTR gene
2. Subjects with only 1 mutation in the CFTR gene **and** a sweat chloride test  $\geq 60$  mM by quantitative pilocarpine iontophoresis.
  3. History of any organ transplantation or lung resection or chest wall surgery.
  4. Significant congenital heart defects, other than a laterality defect, at the discretion of the investigator.
  5. Diagnosis of Cri du chat syndrome (chromosome 5p deletion syndrome).
  6. Inability to withhold short-acting bronchodilator use for 4 hours prior to clinic visit and long-acting bronchodilator use the night before the first and last clinic visit of each treatment period.
  7. History of any illness or any clinical condition that, in the opinion of the investigator, might confound the results of the study or pose an additional risk in administering study drug(s) to the subject. This may include, but is not limited to history of clinically significant and uncontrolled adrenal, neurologic, gastrointestinal, renal, hepatic, cardiovascular (including hyper/hypotension and tachy/bradycardia), psychological, pulmonary (other than PCD), metabolic, endocrine, or hematological/coagulation disorder or disease, or scoliosis of such severity that it impacts pulmonary function or any other major disorder or disease, in the opinion of the investigator.
  8. Use of diuretics (including amiloride) or renin-angiotensin antihypertensive drugs (e.g., spironolactone, angiotensin converting enzyme [ACE] and/or neural endopeptidase [NEP]-inhibitors, or angiotensin receptor blockers [ARBs]) or trimethoprim or drosipironone in the 28 days before Day 1 or anticipate need for these medications during the study.
  9. Had symptoms of acute upper or lower respiratory tract infection or had an acute pulmonary exacerbation requiring treatment or was treated with systemic antibiotics for ear or sinus disease within 28 days before Day 1 (topical otic antibiotics allowed).
  10. History of significant intolerance to inhaled HS, as determined by the investigator.
  11. History of drug or alcohol abuse, in the opinion of the investigator.
  12. Known hypersensitivity to any of the study drugs or amiloride.
  13. Used ivacaftor within 28 days prior to Day 1 or anticipate need for ivacaftor during the study.
  14. Pregnant and/or nursing females.
  15. Any clinically significant laboratory abnormalities at the Screening Visit as judged by the investigator, or any of the following:
    - a. Plasma or serum potassium > upper limit of normal (ULN)
    - b. Abnormal renal function, defined as creatinine clearance rate <50 mL/min using the Bedside Schwartz equation (for subjects 12 to 17 years of age) or <50 mL/min using the Cockcroft-Gault equation (for subjects  $\geq 18$  years of age).

- c. Abnormal liver function, defined as  $\geq 3 \times$  ULN for alanine aminotransferase (ALT) or aspartate aminotransferase (AST), or  $> 2 \times$  ULN for total bilirubin, unless accounted for by Gilbert's syndrome (benign indirect hyperbilirubinemia)
  - d. Hemoglobin concentration  $< 10.0$  g/dL
16. Unwilling or unable to follow the contraception guidelines as outlined in [Section 11.6.5.1](#).
  17. History of at least 2 sputum or throat swab cultures yielding *B. cepacia* complex or *M. abscessus* or *M. avium* within the previous 2 years.
  18. Has had surgery within 3 months of Day 1 that required general anesthesia and hospitalization.
  19. Has previously participated in an investigational study involving administration of any investigational compound or use of an investigational device within 28 days prior to the Screening Visit (Note: Participation in a past or concurrent observational study is acceptable).
  20. Has any surgical or medical condition which in the judgment of the investigator might interfere with the absorption, distribution, metabolism, or excretion of the study drug or with safety evaluations.
  21. Has any other condition or circumstances that, in the opinion of the investigator, should disqualify this subject for this study.
  22. The subject or a close relative of the subject is the investigator or a sub-investigator, research assistant, pharmacist, study coordinator, or other staff directly involved in the conduct of the study.

### 9.2.1 Additional Exclusion Criteria for Part B

In addition to the exclusion criteria above, subjects who participate in Part B and meet any of the following exclusion criteria will **not** be eligible to continue into Part B.

1. Unable to swallow tablets.
2. Concomitant use of strong or moderate inhibitors or inducers of cytochrome P450 (CYP) 3A, including consumption of certain herbal medications (e.g., St. John's Wort), and grapefruit/grapefruit juice.
3. Known hypersensitivity to ivacaftor.

### 9.3 Study Restrictions

Prohibited and restricted medications are not allowed in this study (Screening Period through the last study visit) as summarized in [Table 9-1](#) and [Table 9-2](#).

**Table 9-1 Prohibited Medications**

| Prohibited Medication  | Screening Period                                     | Part A   |  |  | Part B             |  | Until Safety Follow-Up Telephone Call |
|--|--|--|--|--|--------------------|--|---------------------------------------|
|  |  | Treatment Period 1                                   | Washout Period                                       | Treatment Period 2                                   | Treatment Period 3 |  |                                       |
| 
 
• Hypertonic saline
 
• Diuretics (including amiloride)
 
• Renin-angiotensin antihypertensive drugs (ACE and/or NEP-inhibitors or ARBs)
 
• Trimethoprim
 
• Drospirenone
 
 | None allowed within 28 days before Day 1             | None allowed   | None allowed   | None allowed   | None allowed       | Used as prescribed by subject's health care provider   |                                       |
| Medications with moderate or potent CYP3A inhibitor activity, as well as grapefruit/ grapefruit juice  | Used as prescribed by subject's health care provider | Used as prescribed by subject's health care provider | Used as prescribed by subject's health care provider | Used as prescribed by subject's health care provider | None allowed       | Used as prescribed by subject's health care provider beginning 48 hours after the subject's last dose of ivacaftor |                                       |
| Moderate or potent CYP3A inducers including certain herbal medications such as St. John's Wort   | Used as prescribed by subject's health care provider | Used as prescribed by subject's health care provider | Used as prescribed by subject's health care provider | Used as prescribed by subject's health care provider | None allowed       | Used as prescribed by subject's health care provider beginning 48 hours after the subject's last dose of ivacaftor |                                       |

**Table 9-2 Antibiotic and Bronchodilator Restrictions**

| Restricted Medication                  | Screening Period  | Part A   |  |   | Part B   |  | Until Safety Follow-up Telephone Call                |
|--|---|--|--|---|--|--|--|
|  |   | Treatment Period 1   | Washout Period   | Treatment Period 2  | Treatment Period 3   |  |  |
| Chronic or chronic cycling antibiotics | Must have been on a consistent regimen for at least 4 months prior to the Screening Visit                                   | Must remain on the pre-study regimen   | Must remain on the pre-study regimen   | Must remain on the pre-study regimen  | Must remain on the pre-study regimen   | Must remain on the pre-study regimen   | Used as prescribed by subject's health care provider |
| Long-acting bronchodilators            | Should be used at the same time of day, on the same schedule as during the 28 days before Day 1, unless medically necessary | Should be used at the same time of day, on the same schedule, every day

Must be withheld the night before the clinic visit on Day 1 and Day 29, unless medically necessary. | Should be used at the same time of day, on the same schedule, every day

Must be withheld the night before the clinic visit on Day 57, unless medically necessary. | Should be used at the same time of day, on the same schedule, every day

Must be withheld the night before the clinic visit on Day 57 and Day 85, unless medically necessary. | Should be used at the same time of day, on the same schedule, every day

Must be withheld the night before the clinic visit on Day 85 and Day 113, unless medically necessary. | Should be used at the same time of day, on the same schedule, every day

Must be withheld the night before the clinic visit on Day 85 and Day 113, unless medically necessary. | Used as prescribed by subject's health care provider |
| Short-acting bronchodilators           | Must be withheld for 4 hours prior to spirometry performed at the clinic visit, unless medically necessary                  | Must be withheld for 4 hours prior to spirometry performed at the clinic visit, unless medically necessary   | Must be withheld for 4 hours prior to spirometry performed at the clinic visit, unless medically necessary   | Must be withheld for 4 hours prior to spirometry performed at the clinic visit, unless medically necessary  | Must be withheld for 4 hours prior to spirometry performed at the clinic visit, unless medically necessary   | Must be withheld for 4 hours prior to spirometry performed at the clinic visit, unless medically necessary   | Used as prescribed by subject's health care provider |

**9.4 Prior and Concomitant Medications**

Subjects are to remain on a stable PCD medication regimen from 28 days before Day 1 through the last study visit. Those patients taking HS before the Screening Period will washout from HS during the Screening Period and will not be allowed to take HS for the duration of the study

through the end of the last study visit (other than as blinded study drug if allocated to an HS-containing treatment sequence).

The following guidelines for bronchodilator use should be adhered to:

- Throughout the study, short- and long-acting bronchodilators should be used on the same time of day and schedule as during the 28 days before Day 1.
- Short-acting bronchodilators must be withheld for 4 hours prior to spirometry performed at the clinic visit and long-acting bronchodilators must be withheld the night before each clinic visit. Short- and long-acting bronchodilators may be taken by the subject if medically necessary.

Information regarding all prior and concomitant medications, including the subject's PCD medications, other medications, and herbal and naturopathic remedies administered from 28 days before the Screening Visit through the Safety Follow-up Telephone Call will be recorded in each subject's source documents and electronic case report form (eCRF). For subjects who are screened but are not subsequently enrolled into the study, details of prior medication will only be documented in the subject's source documents.

#### **9.4.1 Prohibited Medications in Part B**

Prohibited and restricted medications are described in [Table 9-1](#) and [Table 9-2](#).

Subjects who participate in Part B must not use medications with moderate or potent cytochrome P450 (CYP)3A inhibitor or inducer activity, and should not use certain herbal medications, grapefruit, or grapefruit juice beginning on Day 85 until 48 hours after the last dose of ivacaftor.

Subjects must not use commercially-available ivacaftor during the study.

A comprehensive list of restricted medications will be provided in the Study Reference Manual. Noncompliance with these restrictions will be addressed on a case-by-case basis with the Parion medical monitor.

#### **9.5 Removal of Subjects**

Subjects may withdraw from the study at any time at their own request. Subjects may be withdrawn from study drug treatment at any time at the discretion of the investigator or Parion Sciences for safety, behavior, noncompliance with study procedures, or administrative reasons. If a subject has been withdrawn from study drug treatment, the subject will continue to be followed, provided the subject has not withdrawn consent.

Subjects who discontinue study drug early should continue to return for study assessments, as noted in [Section 8.1.5](#).

If a subject does not return for a scheduled visit, reasonable effort will be made to contact the subject. In any circumstance, reasonable effort will be made to document subject outcome. The investigator will inquire about the reason for withdrawal, request that the subject return all unused investigational product(s), request that the subject return for an ETT Visit, if applicable (see [Section 8.1.5](#)), and follow up with the subject regarding any unresolved AEs. The site staff should perform the Safety Follow-up Telephone Call with the subject 28 days ( $\pm$  7 days) after the last dose of study drug.

If the subject withdraws consent for the study, no further evaluations will be performed and no additional data will be collected. Parion Sciences may retain and continue to use any data collected before such withdrawal of consent.

**A subject will be withdrawn from study drug for any of the following reasons:**

- Parion Sciences, regulatory authorities, or the site's institutional review board (IRB) or independent ethics committee (IEC) close the study.
- A female subject or a female partner of a male subject has a confirmed pregnancy.
- A subject has persistent and severe bronchospasm related to study drug administration.
- A subject's treatment is unblinded by the investigator.
- Development of a life-threatening AE or a serious adverse event (SAE) that places him/her at immediate risk, and discontinuation of study drug deemed necessary.

**A subject may be withdrawn from study drug after a discussion between the investigator and the Parion medical monitor for any of the following reasons:**

- Development of a medical condition that requires prolonged concomitant therapy with a prohibited medication or prolonged interruption of the study drug.
- Noncompliance with study requirements.
- A serum potassium level  $>1.1 \times \text{ULN}$ , confirmed by a plasma potassium level  $>1.1 \times \text{ULN}$ . A confirmatory serum and plasma potassium level may be drawn at the discretion of the investigator before making the decision to remove a subject from the study. Refer to [Section 11.6.2.1](#) for further guidance on treatment of hyperkalemia.
- The subject has a relative decline in  $\text{ppFEV}_1$  of  $\geq 15\%$  from their Day 1, Day 57, or Day 85 Visit pre-dose value.
- An increase in ALT or AST according to evaluations and management described in [Section 11.6.2.2](#).

## **9.6 Replacement of Subjects**

Subjects who withdraw or are withdrawn during the study drug treatment period(s) or washout period will not be replaced.

## **10 STUDY DRUG ADMINISTRATION AND MANAGEMENT**

### **10.1 Preparation and Dispensing**

Study drug may be dispensed only under the supervision of the investigator or an authorized designee and only for administration to the study subjects.

### **10.2 Administration**

#### **10.2.1 Inhaled Study Drug Administration Via the Nebulizer**

Inhaled study drug will be administered twice daily by a PARI eFlow nebulizer. The nebulizer will be provided to the subject for use with the inhaled study drug, and has been customized to be used *only* with the inhaled study drug provided for this study and is not to be used for the

inhalation of other treatments. Additionally, it is important that the subject use the provided nebulizer for the inhalation of study drug and not use any other PARI eFlow nebulizer devices that they may have.

Subjects will be given instruction by the site staff on the proper use and care of the nebulizer, and will also receive written instructions on the care, use, and cleaning requirements. The nebulizer device (nebulizer and handset/aerosol head) identification information will be documented for each subject.

Subjects are required to use the correctly assembled device, into which inhaled study drug has been added, and to nebulize through oral inhalation sitting up, with the device held horizontally and breathing more deeply than normal tidal breathing. This should be continued until all study drug has been delivered.

A replacement nebulizer and/or handset (aerosol head) may be provided at other times during the study, if necessary.

### **10.2.2 Ivacaftor**

For subjects enrolled in Part B of the study, the first dose of oral ivacaftor will be administered at the Day 85 Visit. A fat-containing meal or snack will be provided for ivacaftor dosing at the clinic. Subjects are required to take 150 mg of ivacaftor orally q12h with fat-containing food, such as a high-fat, high-calorie meal or snack. Examples of appropriate fat-containing foods will be provided in the Study Reference Manual.

### **10.2.3 Dosing in Clinic**

This study requires that the first dose of study drug during each Treatment Period be taken in the clinic (at the Day 1, Day 57, and Day 85 Visits) while the subject is under observation by the study staff for at least 1 hour after dosing.

The post-dose observation period is generally anticipated to encompass the first hour after dosing at Day 1 and Day 57, at which time spirometry, chest auscultation, pulse oximetry, and vital signs will be repeated. If the subject is doing well and is in no respiratory distress, the subject will be allowed to leave the clinic after this period and will be given 28 days of the study drug for at-home administration. If, however, in the judgment of the investigator, the subject needs to continue to be observed or monitored, the length of the post-dose observation period may be extended.

Until the IDMC allows a 1-hour post-dose observation period at Day 85, subjects who continue into Part B will remain in clinic during the Day 85 Visit for 2 to 4 hours after administration of study drug. The amount of time each subject remains in clinic for observation (2 to 4 hours) may be left up to the discretion of the investigator. Prior to discharge, spirometry, chest auscultation, pulse oximetry, and vital signs will be repeated. If the subject is doing well and is in no respiratory distress, the subject will be allowed to leave the clinic after this period and will be given 28 days of the study drug for at-home administration. If, however, in the judgment of the investigator, the subject needs to continue to be observed or monitored, the length of the post-dose observation period may be extended.

If the subject routinely uses a short-acting bronchodilator prior to any inhalation treatment(s) (i.e., pre-treat), this practice should be continued throughout the study prior to inhalation of the inhaled study drug. If the subject does not routinely pre-treat inhaled medications with a short-

acting bronchodilator, but has demonstrated significant respiratory symptoms after the test-dose of HS at the Screening Visit, as determined by the investigator or an absolute decline in ppFEV1 of  $\geq 15$  percentage points following the first dose of blinded inhaled study drug at Day 1, then the subject should be provided with a short-acting bronchodilator, as needed, and instructed to subsequently pre-treat with this medication prior to all subsequent doses of blinded inhaled study drug.

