o The ECG will be performed after the subject has been seated or supine for at least 5 minutes. Prior to placing ECG leads, the record will be reviewed for the presence of dextrocardia. Subjects with dextrocardia will have all ECG limb and chest (V) leads reversed.

p Spirometry will be performed prior to dosing with study drug and 1 hour post-dose at the Day 1 and Day 57 Visits. At the Day 85 Visit, if the subject continues into Part B, spirometry will be performed pre-dose and post-dose, prior to discharge from the clinic. If the subject does not continue into Part B, spirometry will only be performed once at the Day 85 Visit.

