**Table 8-1 Study PS-G202 Treatment Sequences**

| Sequence | Part A                 |                        | Part B                             | N  |
|----------|------------------------|------------------------|------------------------------------|----|
|          | Treatment Period 1     | Treatment Period 2     | Treatment Period 3                 |    |
| 1        | VX-371 in 4.2% HS      | 4.2% HS                | 4.2% HS + ivacaftor                | 50 |
| 2        | 4.2% HS                | VX-371 in 4.2% HS      | VX-371 in 4.2% HS + ivacaftor      | 50 |
| 3        | VX-371 in 0.17% saline | Placebo (0.17% saline) | Placebo (0.17% saline) + ivacaftor | 25 |
| 4        | Placebo (0.17% saline) | VX-371 in 0.17% saline | VX-371 in 0.17% saline + ivacaftor | 25 |

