### 8.1.2 Screening: Day -38 to Day -5

Screening Visit assessments are listed in [Table 3-1](#).

The Screening Visit will occur between Day -38 and Day -5 before administration of the first dose of inhaled study drug to confirm that the subject meets the inclusion and exclusion criteria for the study. The investigator (or an appropriate authorized designee at the study site) will obtain informed consent and assent (where applicable) from each subject. To prepare for study participation, subjects will be instructed on the study requirements for concomitant medications ([Table 9-1](#) and [Table 9-2](#)).

At the Screening Visit, each subject will receive a test dose of 4.2% HS via a PARI eFlow nebulizer to confirm tolerability of inhaled HS. Pre-dose spirometry will be performed within 60 minutes before the test dose. Post-dose spirometry will be performed 60 ( $\pm$  5) minutes after the test dose. If the subject's post-HS test dose spirometry value shows a 15-percentage point or

greater absolute reduction in ppFEV1 compared to the subject's pre-HS test dose ppFEV1 value, the investigator may either screen fail the subject or administer a short-acting bronchodilator to the subject.

If the subject is treated with a short-acting bronchodilator, spirometry will be repeated at least 10 minutes after administration of the short-acting bronchodilator. If the subject's post-short-acting bronchodilator ppFEV1 value does not return to within 15 percentage points (absolute) of the subject's pre-HS test dose ppFEV1 value, the investigator should screen fail the subject.

If the subject's ppFEV1 returns to within 15 percentage points (absolute) of the pre-HS test dose value, the investigator may provide a short-acting bronchodilator for use before all doses of inhaled study drug are administered.

If the subject experiences a post-HS test dose absolute decline in ppFEV1 less than 15 percentage points, the investigator may choose to provide a short-acting bronchodilator for use before all doses of inhaled study drug are administered.

While subjects can be screened based on evidence supportive of a PCD diagnosis, all subjects must meet the confirmatory diagnostic PCD criteria (including central review, as required) prior to randomization ([Section 9.1](#)).

Screen failures and reason for failure will be documented within the eCRF.

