7.5.2 Concomitant Medication

[figure not shown]
Concomitant medication is defined as any medication that is continued or newly received during the Treatment-Emergent (TE) period for Part A, or Part B.

A medication that starts/ends on or after the start date of the Treatment Emergent Period, up through and before the start date of the next Treatment Emergent Period, will be assigned to the treatment group associated with the current Treatment Emergent Period.

For the cases when Treatment Emergent Period 2 end of dosing is on the same day as the Treatment Emergent Period for Part B start of dosing date, any medication starting on the same day as the Treatment Emergent Period for Part B start of dosing date, will be assigned to the treatment in Period for Part B.

1006696
Parion Sciences Incorporated
CLEAN-PCD
SAP Version 1.0

A given medication can be classified as a prior medication, a concomitant medication, or both prior and concomitant. If a medication has a missing or partial missing start/end date and it cannot be determined whether the medication was taken before initial dosing or concomitantly, it will be considered as prior and concomitant, and this medication will be assigned to all treatment groups.

If the start date of the medication is the same as the date of the first dose date of the study drug in Period 1, then the medication is classified as a concomitant medication and will be assigned to Period 1 treatment group.

Concomitant medications will be summarized by ATC level 1 and 2 term and preferred term (PT). Part A concomitant medications will be summarized by treatment based on the Part A FAS, and Part B concomitant medications will be summarized by treatment based on the Part B FAS.

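### The 15-point ppFEV1 trigger for bronchodilator pre-treatment (Protocol 10.2.3) covers the Day 1 dose only, although half the planned subjects first inhale VX-371 on Day 57

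*Protocol*

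**What the plan says.** Protocol 10.2.3 has the first dose of each Treatment Period taken in clinic. For subjects who do not routinely pre-treat inhaled medication, it gives two triggers for starting. One is significant respiratory symptoms after the Screening test dose. The other is an absolute ppFEV1 fall of 15 points or more "following the first dose of blinded inhaled study drug at Day 1, then the subject should be provided with a short-acting bronchodilator", to be used as needed and then before all later inhaled doses. Neither trigger refers to Day 57.

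Other relevant text:

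- **Screening (8.1.2).** The test dose is hypertonic saline (HS) alone: "each subject will receive a test dose of 4.2% HS via a PARI eFlow nebulizer to confirm tolerability of inhaled HS". If the fall is under 15 points, "the investigator may choose to provide a short-acting bronchodilator for use before all doses of inhaled study drug are administered".
- **Sequences (Table 8-1).** Sequence 2 takes HS and then VX-371 in HS. The Part A entries for sequence 4 are "Placebo (0.17% saline) | VX-371 in 0.17% saline". Both start VX-371 at the Day 57 visit (8.1.3.1.3).
- **Measurement (Table 3-2, footnote p).** "Spirometry will be performed prior to dosing with study drug and 1 hour post-dose at the Day 1 and Day 57 Visits".
- **Default schedule (9.4).** "short- and long-acting bronchodilators should be used on the same time of day and schedule as during the 28 days before Day 1", with an allowance for medical need.

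**The concern.** Subjects in sequences 1 and 3 who react to their first VX-371 dose on Day 1 are told to pre-treat from then on. Subjects in sequences 2 and 4 meet VX-371 for the first time on Day 57. Neither trigger in 10.2.3 can detect a VX-371 reaction in them: the Screening dose has no VX-371, and their Day 1 dose is HS or placebo. The spirometry that would show the fall is already scheduled, but no pre-treatment advice is attached to it.

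The stake is patient safety and, to a lesser degree, retention. The one step the protocol ties to the size of a Day 57 fall is a discussion about withdrawing study drug (9.5). The less drastic response is written for Day 1 only, and 28 days of twice-daily home dosing follow Day 57.

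**Working it through.** **1. Who first inhales VX-371 on Day 57.** The allocation is 2:2:1:1 of about 150 (10.3): 150 × 2/6 = 50, 50, and 150 × 1/6 = 25, 25. This reproduces Table 8-1. Sequences 2 and 4: 50 + 25 = 75, or 75/150 = 50%.

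**2. What covers a Day 57 fall.**

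| Provision | Applies on or after Day 57? | Advises pre-treating and continuing? |
|---|---|---|
| 10.2.3 spirometric trigger | No, Day 1 only | Yes |
| 10.2.3 discharge condition, extended observation | Yes | No |
| 9.4 bronchodilator use for medical need | Yes | No, permits use only |
| 10.4 dose interruption after medical monitor discussion | Yes | No |
| 8.1.3.1.3 Day 60 safety call | Yes | No |
| 9.5 mandatory withdrawal, persistent and severe bronchospasm | Yes | No |
| 9.5 possible withdrawal, relative fall of 15% or more | Yes, Day 57 is named | No |

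**3. Overlap with 9.5.** A 15-point absolute fall is at least 15% in relative terms for any pre-dose value up to 100: 15/100 = 15.0%, 15/90 = 16.7%, 15/40 = 37.5%. Screening entry requires ppFEV1 from 40 to under 90 (9.1). A fall that would meet the 10.2.3 trigger therefore also opens the withdrawal discussion for any pre-dose value up to 100.

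**4. How many could be affected.** The documents give neither a reaction rate nor the share already pre-treating, so both are assumed.

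- If the whole assumed 10% dropout (12.1) falls before Day 57: 75 × 0.90 = 67.5.
- Already pre-treating (routine users, those given a bronchodilator at Screening, Day 1 reactors), assumed 0% to 50%: 67.5 down to 67.5 × 0.50 = 33.75, so about 34 to 68 remain.
- Assumed reaction rate 2% to 5%: 33.75 × 0.02 = 0.7 to 67.5 × 0.05 = 3.4, so about 1 to 3 subjects.
- Chance of at least one: 1 − 0.98^33.75 = 49% to 1 − 0.95^67.5 = 97%.

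**5. What the fix could do to SGRQ.** Protocol 8.2.3 says: "A minimum change in score of 4 units was established as clinically relevant after patient and clinician testing". Suppose each affected subject gains 4 units from pre-treatment, in Period 2 of sequences 2 and 4 only. The mean shift in those cells is rate × 4. Under the treatment-plus-period model, half goes to the period effect and half to treatment, so each VX-371 contrast moves by rate × 4 / 2: 0.02 × 4 / 2 = 0.04 units to 0.05 × 4 / 2 = 0.10 units. A generalised least squares fit with compound symmetry and 50/50/25/25 subjects gives the same values at within-subject correlations of 0, 0.5 and 0.8. Against 4 units this is 1% to 2.5%.

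**The case against.** The strongest reply is that the protocol already protects a Day 57 reactor. The subject goes home only if well and free of respiratory distress, a call follows about three days later, dosing can be interrupted, and 9.4 permits a bronchodilator when medically needed. All subjects inhale HS at Screening and sequence 2 inhales it throughout Period 1, so the only new exposure on Day 57 is VX-371. No visible text says that it provokes bronchoconstriction, and part of the dose rationale (8.2.2) is redacted. On this view only an explicit recommendation is missing, itself qualified by need. The SAP would also make reactors visible: 8.1 summarises the pre- to post-dose change on the first day of each period, and 10.6 counts falls of 10, 15 and 20 points or more.

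Much of this stands. A reader might infer that Day 57 reactors are left unprotected; the table above shows otherwise. The figure of 75 counts subjects newly exposed, not subjects at risk. What remains is narrower: the protocol wrote a rule for this situation and its wording misses half of the planned first VX-371 exposures. SAP summaries come too late to guide a site on the day.

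A second reply is that a Day 1-only trigger treats both Part A periods alike, whereas a Day 57 start brings a new bronchodilator regimen into Period 2 alone. That is a defensible crossover argument and a real cost of the change. A reader might infer that it is why the rule was written so, but the documents do not give that reason.

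**Conclusion.** The gap is real and small. No section advises starting pre-treatment and continuing after a Day 57 fall, and 75 of 150 planned subjects first meet VX-371 that day. At the assumed rates about 1 to 3 subjects would be affected; the true number is unknown because no reaction rate is given.

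Two stronger readings are not supported. First, a reader might infer unequal treatment of the arms; the limit is by period and all four sequences share it. Second, a reader might infer bias in the efficacy result. Power and the primary ppFEV1 comparison are not materially affected: few subjects are involved, and short-acting bronchodilators are withheld for 4 hours before spirometry. The SGRQ shift of 0.04 to 0.10 units illustrates the cost of the fix only. It is not a bound, because the rate and the 4-unit gain are both assumed and no Day 57 starters are assumed in sequences 1 and 3.

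This is a minor safety improvement, worth considering.

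**What to change.** In 10.2.3, change *at Day 1* to *at Day 1 or Day 57*. Day 85 need not be added for the inhaled drug, because Part B continues the Period 2 inhaled treatment. State that pre-treatment started on Day 57 is an accepted exception to the fixed schedule in 9.4.

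Report how many subjects start pre-treatment on Day 57, by sequence, beside the SGRQ, QOL-PCD and AE results. Medication dates are already collected (9.4), and SAP 7.5.2 already captures new starts: "Concomitant medication is defined as any medication that is continued or newly received during the Treatment-Emergent (TE) period for Part A, or Part B". For subjects who already hold a short-acting bronchodilator, dates alone may not separate pre-dose from rescue use, so sites should record the reason for the change.

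The change needs a few words and no new visit or test. Its cost is that a few subjects would pre-treat in Period 2 only, which in sequences 2 and 4 is the VX-371 period. The 4-hour withholding rule limits the effect on Day 85 ppFEV1 but does not protect SGRQ, QOL-PCD or AEs. That is the reason for reporting the count.
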